1.3 Pre-Clinical & Clinical Experience with Investigational Medicinal Product (IMP)

Doxycycline is a well-known drug with a good safety profile used for several infectious diseases worldwide.

1.4 Rationale for the Study and Purpose

The main purpose of the trial is to answer the “is two weeks doxycycline treatment (currently suggested treatment) at least as effective as six weeks doxycycline treatment in LNB?” The benefits of a positive answer to this question would

be a reduced frequency of persisting complaints after treatment. The benefits of a negative answer would be avoidance of unnecessarily prolonged treatment with antibiotics and thereby reduced antibiotic resistance. Doxycycline 200 mg daily for 2 weeks is recommended for LNB, and half of the study patients will receive this standard treatment (and additional four weeks of placebo). The other half will receive doxycycline 200 mg daily for six weeks. Possible disadvantages for the trial participants are more adverse advents as nausea and diarrhea, disturbances in leukocyte and thrombocyte count, and skin reactions (mostly photosensitivity). Longer antibiotic treatment may also lead to higher prevalence of resistant bacteria in patients and the general society. We regard these possible disadvantages as minor as the patients' subjective experiences and blood cell count will be closely monitored during the study, and both groups of patients will be discouraged sunbathing during treatment and up to two weeks after drug intake. In our opinion, the benefit of determination of preferred duration of treatment for the future eliminates the disadvantage of exposing. Besides this, several spin off effects strengthens the rationale for conducting the study. The collected clinical data and specimens (blood and CSF) from well-characterized LNB patients may enable us to address other hypotheses regarding long-term complaints as immune dysregulation, genetic predisposition, co-infections and structural changes in CNS, and it facilitates search for new biomarkers of LNB which could be used in diagnostics.

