1.2 Background - Therapeutic Information

Standard treatment for Lyme Neuroborreliosis (LNB) is intravenous ceftriaxone or penicillin, or oral doxycycline for two to four weeks (1). Previous studies have shown that two weeks of oral doxycycline and intravenous ceftriaxone are equally effective for LNB with painful radiculitis or cranial neuritis (5, 18). However, evidence about the optimal duration of treatment is currently lacking. There are a few studies of prolonged antibiotic treatment in LNB, but they are hampered with poorly-characterized patients, insufficient statistical power, lack of matched controls, and ambiguous results (19-23). A case series reported excellent or good response in 90% of patients with disseminated Lyme (including some with neuroborreliosis) after treatment with oral cefixime or IV ceftriaxone for 14 days followed by oral amoxicillin for 100 days (24). A controlled study of 152 patients with disseminated Lyme disease (including 62 with neuroborreliosis) (20), however, found similar outcome in patients treated with 3 weeks with IV ceftriaxone followed by oral amoxicillin for 100 days and patients treated with 3 weeks IV ceftriaxone followed by placebo for 100 days. An American openlabel randomized comparison of 14-days versus 28-days treatment with ceftriaxone for late Lyme borreliosis (143 patients, of whom a third with neurological symptoms), showed more treatment failures in the 14-day group than in the 28-day group, but did not have the power to determine if a clinical subset of patients may benefit from 28 days of therapy. There were more discontinuations because of adverse events in the 28- days group (25). Another series of late LNB showed disappearance of symptoms in 87% after 100 days regimens with various antibiotics, whereas 14 days with ceftriaxone cured 31% (26).

The possibility that a longer treatment with doxycycline, such as six weeks, is superior to the current standard treatment of two weeks in LNB has not been properly addressed in a randomized controlled trial.

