3 OVERALL STUDY DESIGN

The study is a phase Phase III, randomized, penta-blind, placebo-controlled, multicenter trial with a non-inferiority design. The trial will be conducted and reported according to the CONSORT statement (Consolidated Standards of Reporting Trials), the SPIRIT initiative (Standard Protocol Items: Recommendations for Interventional Trials), and Good Clinical Practice (GCP) standards, and registered in ClinicalTrials.gov

Study Period	Estimated date of first patient enrolled: 01.10.15 (startup at Sørlandet Hospital 2015, recruitment from other centres gradually during 2016)
	Anticipated recruitment period: 01.10.15 - 31.12.19
	Estimated date of last patient completed: 31.12.20
Treatment Duration:	Six weeks
Follow-up:	13 months

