10 STATISTICAL METHODS AND DATA ANALYSIS

10.1 Determination of Sample Size ** [name]?

In a previous trial on well-characterized LNB patients, 102 patients were treated with either oral doxycycline or IV cephtriazone for two weeks. From this trial we have available outcome scores at 12 months from 93 patients, measured on a slightly different composite clinical scale, but with the same max score of 64. We consider the scales as so similar that the results from the former trial can be used in power analyses in the current planned trial. The mean score in the former trial was 1.7 with a standard deviation (SD) of 2.6.

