10.5 Statistical Analysis **[name]?

Results will be reported as mean scores with standard deviation or proportions as appropriate.

To compare the two groups on the primary outcome, we will use a general linear model with treatment group was factor and adjust for duration of symptoms, gender and age. The analysis will be conducted according to the intention to treat principle.

For other analysis, comparison between groups will be done with e.g. independent samples t-test, nonparametric Mann-Whitney-U test or Pearsons chi-square test for crosstabs as appropriate.

P-values <0.05 are considered statistically significant.

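### The trial is declared non-inferiority, but its only stated criterion is P<0.05 for a difference, with no margin or confidence-limit rule, and section 1.4 reverses what a yes and a no would mean

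*Combined protocol and SAP*

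**What the plan says.** The synopsis, Table 1 and section 1.4 put the same primary question: "is two weeks doxycycline treatment (currently suggested treatment) at least as effective as six weeks doxycycline treatment in LNB". The synopsis and section 3 ("multicenter trial with a non-inferiority design") declare a non-inferiority trial.

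Section 1.4 then says what each answer would bring. For a positive answer, the benefit would "be a reduced frequency of persisting complaints after treatment". For the other: "The benefits of a negative answer would be avoidance of unnecessarily prolonged treatment". Section 1.2 closes by saying that whether a longer course "is superior to the current standard treatment of two weeks in LNB has not been properly addressed in a randomized controlled trial".

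For the primary outcome, section 10.5 specifies a general linear model with treatment group as factor, adjusted for symptom duration, gender and age, on the intention-to-treat principle. It states no hypothesis. The section ends with "P-values <0.05 are considered statistically significant".

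Section 10.1 describes the earlier trial and stops at "The mean score in the former trial was 1.7 with a standard deviation (SD) of 2.6". It gives no margin, power or dropout allowance, and nothing marks text as withheld there. Section 4.2 plans 60 patients per arm.

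**The concern.** A non-inferiority claim needs a margin and a rule that excludes a deficit as large as that margin. A P<0.05 comparison of two means does neither. A significant result in favour of two weeks would answer the question, but as a finding of superiority. A non-significant result leaves it open, because it is compatible both with equivalence and with a real deficit that the trial was too imprecise to detect.

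Section 1.4 is where the document spells out the benefit attached to each answer, and it does so the wrong way round. A yes to the stated question is the answer that spares patients a longer course. A no leaves open that longer treatment reduces complaints. The text as written fits a different question, whether six weeks is better, which is where section 1.2 ends.

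Put beside a P<0.05 criterion, the text lets a non-significant difference pass as the negative answer that justifies avoiding prolonged treatment. The risk of accepting a shorter course that is truly worse would then not be controlled at any stated level.

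**Working it through.** **Direction of the answers**

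| Answer to the stated question | What follows logically | What section 1.4 attaches |
|---|---|---|
| Yes, two weeks is at least as effective | Longer treatment can be avoided | Fewer persisting complaints |
| No | Longer treatment may reduce complaints | Longer treatment can be avoided |

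The two entries in the last column are exchanged.

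**Planned sample size.** The figure of 120 cannot be reproduced, because margin, power and dropout are not stated. Several assumed sets give it with SD 2.6 and a true difference of zero:

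- margin 1.33, 80% power, one-sided 0.025, no dropout: 60 per arm, 120 in total;
- margin 1.5, 80% power, one-sided 0.025, 20% dropout: 96 / 0.8 = 120;
- margin 1.25, 80% power, one-sided 0.05, 10% dropout: 108 / 0.9 = 120.

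None of these can be attributed to the plan.

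**How often a real deficit would be non-significant**

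Inputs from the documents: 60 per arm (section 4.2) and SD 2.6 (section 10.1). Assumptions: a two-sided test (sidedness is not stated), normal approximation, no dropout, no covariate adjustment, and the SD carried over to the primary endpoint.

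SE = 2.6 × √(2/60) = 0.475. The 95% CI half-width is 1.96 × 0.475 = 0.93.

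P(non-significant) = Φ(1.96 − d/SE) − Φ(−1.96 − d/SE), where d is the true advantage of six weeks in points.

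| d | P(non-significant), SD 2.6 |
|---|---|
| 0.5 | 82% |
| 0.85 (half of the earlier mean, 1.7 / 2) | 57% |
| 1.0 | 44% |
| 1.5 | 12% |
| 2.0 | 1% |

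For d = 0.85, d/SE = 1.79, so Φ(0.17) − Φ(−3.75) = 0.567. If the SD of the improvement score were 4 (an assumption), the figures at 0.5, 1.0, 1.5 and 2.0 points would be 90%, 72%, 46% and 22%.

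**Margin that 60 per arm supports** (one-sided 0.025, true difference zero)

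(1.96 + 0.84) × 0.475 = 1.33 points at 80% power, and 1.54 at 90%. With SD 4 at 80% power it is 2.05. A margin of 1.0 at SD 2.6 would need 214 patients at 80% power or 286 at 90%, before dropout.

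**Where the two rules part.** Take a margin of 1.33 purely as an example. Non-inferiority requires an observed advantage of six weeks below 1.33 − 0.93 = 0.40. The difference test stays non-significant up to 0.93. An observed advantage between 0.40 and 0.93 would thus be non-significant and yet fail non-inferiority.

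**The case against.** The strongest reply is that section 1.4 is introductory text, while the statements that govern the trial (the synopsis objective and design, Table 1, section 3) are correct and agree with one another. The reversed sentences may simply be left over from the superiority framing of section 1.2. That stands: on its own the reversal is a wording slip and does not show that the trial is really a superiority trial.

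A reader might also infer that the plan would treat a non-significant P-value as proof that two weeks is enough. The document does not say so. Section 1.4 mentions no test, and the P<0.05 sentence in 10.5 is a general closing line that follows the paragraph on other analyses. The linear model could equally supply a confidence interval. So the supportable statement is that a null result could be read that way, because nothing in the plan prevents it.

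The illustration has limits too. The SD of 2.6 belongs to a 12-month score on a slightly different scale, whereas the primary endpoint is improvement at six months. The 0.85 and 1.0-point deficits are chosen for illustration. It would be tempting to add that a 1.33-point deficit is non-significant 20% of the time, but 1.33 is by construction the difference detectable with 80% power, so that figure says nothing particular about this plan.

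Finally, section 10.4 allows the statistical plan to be amended until database lock, so a margin could have been added later. The document under review shows none. What remains after these objections is the gap in section 10.

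**Conclusion.** The concern holds for the decision rule. The trial is declared non-inferiority, but the plan's only criterion is a test for a difference, with no margin and no confidence-limit rule. A non-significant result under that criterion cannot show that two weeks is at least as effective as six. Section 1.4 makes the misreading easier but is a secondary, editorial fault.

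The absence of the rule and the reversal are read directly from the text and need no assumption. The size is illustrative only: about 57% and 44% for true deficits of 0.85 and 1.0 points, conditional on SD 2.6, 60 evaluable patients per arm, a two-sided test and an unadjusted comparison. A larger SD or patient losses would raise these figures. Useful covariate adjustment would lower them.

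**What to change.** 1. In 10.5, for the primary endpoint, state that two weeks is non-inferior if the upper limit of the two-sided 95% CI for the adjusted difference in improvement (six weeks minus two weeks) lies below the pre-specified margin. Add that P≥0.05 for the difference is not evidence of non-inferiority. Keep P<0.05 for secondary comparisons.
2. In 10.1, state and justify the margin, and report the margin that 120 patients can support (about 1.33 points at 80% power under the assumptions above). Fix the margin before any outcome data are seen by group, including as groups A and B. Before unblinding would be too late, because section 10.2.2 has the analysis run and the tables filled with A/B labels before the code is broken.
3. In 1.4, exchange the two consequences.

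The third change is wording only, and the planned model already yields the interval, so no new data are needed. The real cost lies in the margin: it has to be chosen and defended, and the precision available with 120 patients becomes explicit. If the justified margin were as small as 1.0 point, the planned number would fall well short of the 214 needed at 80% power.

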2 STUDY OBJECTIVES AND RELATED ENDPOINTS

	Objectives	Endpoints	Assessments
Primary	To answer the question “is two weeks doxycycline treatment (currently suggested treatment) at least as effective as six weeks doxycycline treatment in LNB?”	
 – Primary endpoint: Improvement of clinical score six months after ended treatment – Secondary endpoints: Fatigue, subjective somatic symptoms, health related quality of life, cognitive function, safety, inflammation. 	
 - Composite clinical score. See section: 2.1 - FSS, PHQ-15, SF-36, adverse events inflammatory parameters in CSF. See section 2.2
Secondary	
 1. To provide a better understanding of the pathogenesis of LNB and long-term complaints 2. To search for new biomarkers in LNB 	
 – Antibody and inflammatory profiles – Genomic profiles – Brain MRI – Neuropsychological profiles 	Described in WP4 of BorrSci. See appendix A
Exploratory	To collect clinical data, blood, and CSF from well-characterized LNB patients in a biobank	
 – Further search for biomarkers, co-infections and other factors involved in LNB 	Described in WP3 of BorrSci. See appendix A

Table 1. Summary of objectives, endpoints, and assessments

2.1 Primary Endpoint

The primary endpoint is improvement on a composite clinical score (Table 2) from inclusion to six months after ended treatment defined as clinical score at inclusion minus clinical score at six months.

Subjective symptoms	
Subjective symptoms related* by the patient to the current/recent LNB	Score
Malaise (sykdomsfølelse, redusert almentilstand)	
Fatigue (trøtthet, utmattelse)	
Headache (hodepine)	
Neck and/or back pain (nakke og/eller ryggsmerte)	
Abdominal and/or breast pain (smerter i bryst og/eller mageregion)	
Arm pain (smerter i armer)	
Leg pain (smerter i ben)	
Generalized pain located to joints and/or muscles (smerter i "hele kroppen" (ledd og muskler))	
Memory and/or concentration problems (hukommelse og/eller koncentrasjonsproblemer)	
Other (annet)	
Objective findings, PNS	
Findings related* to the current/recent LNB	Score
Facial palsy (facialisparese)	
Paresis of eye muscles (øyemuskelparese)	
Reduced hearing (redusert hørsel)	
Other cranial neuropathies (andre hjernenerveutfall)	
Cervical radicular sensory findings ^a (cervikale radikulære sensoriske funn)	
Cervical radicular paresis ^b (cervikal radikulær parese)	
Thoracal radicular sensory findings ^a (thoracale radikulære sensoriske funn)	
Lumbar radicular sensory findings ^a (lumbale radikulære sensoriske funn)	
Lumbar radicular paresis ^b (lumbal radikulær parese)	
Non-radicular sensory findings ^c (ikke-radikulære sensoriske funn)	
Non-radicular paresis ^d (ikke-radikulær nevropati med pareser)	
Other (annet)	
Objective findings, CNS	
Findings related* to the current/recent LNB	Score
Central findings ^e in one extremity (sentralnervøse funn i en ekstremitet)	
Central findings ^e in a hemi pattern (sentralnervøse funn i en kroppshalvdel)	
Central findings ^e in both legs (sentralnervøse funn i begge ben)	
Central findings ^e in all extremities (sentralnervøse funn i alle ekstremiteter)	
Gait ataxia (gangataksi, ustøhet)	
Dysphasi/aphasi (talevansker)	
Nystagmus (nystagmus)	
Involuntary movements including tremor (ufrivillige bevegelser inkl. skjelving)	
Cognitive impairment (kognitiv svikt/forvirring)	
Other (annet)	
Total score	

Table 2. Composite clinical score.

Each item is scored 0=none, 1=mild, without influence on daily life, or 2=severe, with influence on daily life.

Maximum total score=64 (sum of subjective symptoms and objective findings)

* Temporally and otherwise related to current LNB

^a Abnormal sensory findings in a radicular pattern

^b Paresis in a radicular pattern

^c Abnormal sensory findings in a non- radicular pattern (matching with peripheral nerve or plexus)

^d Paresis in a non- radicular pattern (matching with peripheral nerve or plexus)

^e Central weakness and/or spasticity (central paresis, spasticity and/or impairment in pace or fine motor skills)

2.2 Secondary Endpoints

Improvement of composite clinical score from inclusion to 12 months after end of treatment defined as clinical score at inclusion minus clinical score at 12 months. (Table1)

Fatigue Severity Scale (FSS) at six and 12 months after end of treatment. FSS is translated and validated for Norwegian purposes (12). It measures level of agreement (1– 7) with nine statements. The final score represents the mean value of the nine items. Severe fatigue is defined as a score >5 in a Norwegian population. Reported mean score in 20 American

healthy adults is 2.3 (13), and reported mean score in 50 Norwegian patients treated for LNB is 3.5 versus 2.1 in the control group (3).

Patient Health Questionnaire (PHQ-15) at six months. PHQ-15 is a brief, validated questionnaire, which consists of 13 questions concerning severity of different subjective somatic symptoms the last 4 weeks, and 2 questions concerning sleep and tiredness. Each item is scored from 0 to 2, and sum score ranges from 0 to 30. Sum scores of 5, 10, and 15 represent cutpoints for low, medium, and high symptom severity, respectively (27).

Short Form-36 (SF-36): SF-36 is a valid and reliable questionnaire assessing health related quality of life. It consists of 36 questions concerning general health perceptions, physical functioning, physical role functioning, emotional role functioning, social role functioning, bodily pain, vitality and mental health. A Norwegian normal material exist (28).

CSF findings at six and 12 months: Cell count, IgG index, OCB's, and *Bb* antibodies

Other laboratory tests, MRI, and neuropsychological assessments: In a subset of patients at inclusion and six months after end of treatment (WP4 of BorrSci).

Safety as measured by serious adverse events and less serious side effects of treatment (Table 3)

Table 3. Safety measures

Treatmentweek	0	1	2	3	4	5	6	7-10
Nausea		x	x	x	x	x	x	x
Vomiting		x	x	x	x	x	x	x
Diarrhea		x	x	x	x	x	x	x
Skin reactions		x	x	x	x	x	x	x
Vaginitis		x	x	x	x	x	x	x
Blodtests (Hb, Hb, white blood cell count with differential, platelet count, ASAT, ALAT, GT, ALP, Creatinine)	x		x		x			
Other AE or complications		x	x	x	x	x	x	x

Secondary and exploratory objectives and their endpoints and assessments are detailed in WP 3 and 4 (Appendix A)

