Centers:	Sørlandet Hospital + 5-10 other Norwegian hospitals
Study Period:	Estimated date of first patient enrolled: 01.10.15 Anticipated recruitment period: 01.10.15- 31.12.19 Estimated date of last patient completed: 31.12.20
Treatment Duration:	Six weeks
Follow-up:	13 months
Objectives	
Primary objective
 
To answer the question “is two weeks doxycycline treatment (currently suggested treatment) at least as effective as six weeks doxycycline treatment in Lyme Neuroborreliosis?”
 
Key secondary objectives
 
To provide a better understanding of the pathogenesis and long-term complaints, and to search for new biomarkers in LNB
 
To collect clinical data, blood, and CSF in a biobank for future research

Endpoints:	
Primary endpoint:
 
Improvement in composite clinical score defined as clinical score at inclusion minus clinical score at 6 months.
 
Secondary endpoints:
 
Fatigue Severity Scale (FSS) Patient Health Questionnaire (PHQ-15) Short Form 36 (SF-36) Blood and CSF findings MRI, and neuropsychological assessments in a subset of patients Adverse events

Study Design:	Multicenter, non-inferiority, randomized, penta-blind, placebo-controlled trial
Main Inclusion Criteria:	
1. Neurological symptoms suggestive of LNB without other obvious reasons and one or both of
a. Cerebrospinal fluid pleocytosis (≥ 5 leukocytes/mm³)b. Intrathecal Bb antibody production2. Signed informed consent
Main Exclusion Criteria	
- Age less than 18 years- Pregnancy, breast-feeding- Adverse reaction to tetracyclines- Treatment with cephalosporin, penicillin, or tetracycline the last 14 days- Serious liver or kidney disease that contraindicates use of doxycycline- Lactose intolerance- Need to use medications contraindicated according to SmPC of the IMP
Sample Size:	120 patients
Efficacy Assessments:	Comparison of clinical outcome six months after end of treatment between the two treatment groups.
Safety Assessments:	Subjective experiences and blood tests including hematology and biochemistry for four weeks after ended treatment.

TABLE OF CONTENTS

CONTACT DETAILS.....	2
SIGNATURE PAGE	3
PROTOCOL SYNOPSIS.....	4
TABLE OF CONTENTS	5
LIST OF ABBREVIATIONS AND DEFINITIONS OF TERMS.....	8
1 INTRODUCTION.....	9
1.1 Background – Lyme Neuroborreliosis (LNB).....	9
1.2 Background - Therapeutic Information.....	9

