1 INTRODUCTION

1.1 Background – Lyme Neuroborreliosis (LNB)

Lyme borreliosis is a multisystem infectious disease, caused by the tick-borne spirochete *Borrelia burgdorferi* (*Bb*), which frequently affects the nervous system. The most common clinical manifestations of European Lyme Neuroborreliosis (LNB) are painful radiculitis and cranial neuropathy (most often the facial nerve). Rarer manifestations are myelitis, encephalitis, and peripheral neuropathies. The diagnosis of LNB is based on a combination of clinical neurological findings, lymphocytic pleocytosis and intrathecal *Bb* antibody production (1).

Most patients recover well within weeks to a few months after standard antibiotic treatment, but 25-50% of LNB patients report residual complaints often labelled post-Lyme syndrome (2-9). The most common remaining complaints are subjective symptoms as fatigue, pain, concentration and memory problems. Remaining objective findings as facial palsy and radiculopathy are rarer.

The impact and prevalence of post-Lyme syndrome are debated, as similar symptoms are common in the general population. It is also questioned if the complaints are more common after LNB than after other infections in the nervous system. There are few controlled studies on the issue, but one previous study found more fatigue and lower mean scores on health related quality of life among 50 well-characterized LNB patients 30 months after treatment for LNB than among 50 matched healthy controls (3).

The underlying mechanism of post-Lyme syndrome is also debated and largely unresolved. Theories as ongoing chronic *Bb* infection (10), dysregulated immune responses (11, 12), genetic predisposition (13), co-infection with multiple tick-borne pathogens (14), structural changes in the Central Nervous System (CNS) (15), and personal traits (16, 17), have been suggested.

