6.2.1 Screening Visit

- Evaluate patient eligibility based on symptoms, findings and CSF findings
- Demographic data: Age, sex, education, occupational status, civil status
- Medical history: Comorbidity, medication, tick bite (ever and last six months), Erythema Migrans (ever and last six months), earlier treatment for Lyme borreliosis
- Clinical picture: Symptom description, symptom duration
- Physical examination: General clinical and neurological examination including composite clinical score
- Concomitant medication: All concomitant medication (incl. vitamins, herbal preparation and other “over-the-counter” drugs) used by the subject within 28 days of treatment start will be recorded in the CRF.
- Laboratory analysis from samples obtained before inclusion
 - Blood: Hb, white blood cell count with differential, platelet count, ASAT, ALAT, GT, ALP, Creatinine, CRP, electrophoresis, *Bb* antibodies, TBE antibodies. Pregnancy test should have been taken within the last 14 days before inclusion in fertile women.
 - CSF: Cellcount, protein level, Oligoclonal bands, *Bb* antibodies, PCR for Herpes Simplex Virus (HSV), Varicella Zoster Virus (VZV) and Enterovirus
- In addition aliquots of specimens will be transferred for biobank storage after inclusion

- FSS

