6.2.5 Six months After End of Treatment (Follow-up)

- Interview about symptom description, concomitant medication, and sick leave attributable to LNB
- Composite clinical score
- FSS, PHQ-15, SF-36
- Laboratory analyses
 - Blood: Hb, white blood cell count with differential, platelet count, ASAT, ALAT, GT, ALP, Creatinine, CRP, electrophoresis, Bb antibodies, TBE antibodies
 - CSF: Cellcount, protein level, Oligoclonal bands, Bb antibodies,
 - In addition aliquots of specimens will be transferred for biobank storage
- Cerebral MRI and neuropsychological testing in a subset of patients (Appendix A)

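### PHQ-15 and SF-36 have no inclusion value, so change on these two secondary endpoints cannot be computed and some precision in the six-month comparison is lost

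*Combined protocol and SAP*

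**What the plan says.** Section 7.1 names PHQ-15 (somatic symptom burden) and SF-36 (quality of life) among the secondary endpoints chosen to support the assessment of treatment effect. Their timing is as follows.

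- **Section 2.2** sets the "Patient Health Questionnaire (PHQ-15) at six months". For SF-36 it describes the instrument ("SF-36 is a valid and reliable questionnaire assessing health related quality of life") but gives no time point.
- **Section 6.2.1 (screening visit)** lists "General clinical and neurological examination including composite clinical score" and FSS. Neither PHQ-15 nor SF-36 appears.
- **Section 6.2.5 (six months)** lists "FSS, PHQ-15, SF-36". This is the first visit at which PHQ-15 and SF-36 appear.
- **Section 6.2.6 (12 months)** lists FSS and PHQ-15 but not SF-36.
- **Table 5 (flow chart)** agrees with the visit lists: FSS is marked at baseline, PHQ-15 only at six and 12 months, and SF-36 only at six months.

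Section 10.5 adjusts the primary analysis for symptom duration, gender and age. For all other analyses it gives unadjusted two-group tests as examples: t-test, Mann-Whitney and chi-square.

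**The concern.** The primary endpoint and its 12-month counterpart are changes from inclusion, and FSS has an inclusion value that could be used in the same way. PHQ-15 and SF-36 stand apart: the arms can only be compared on raw levels after treatment. That matters more for these scales than for the composite score. The composite score counts only items judged related to the current illness (Table 2 footnote), whereas section 2.2 describes no such filter for PHQ-15 or SF-36. Section 1.1 itself notes that "The impact and prevalence of post-Lyme syndrome are debated, as similar symptoms are common in the general population". Part of the spread in six-month scores will therefore be stable differences between patients that have nothing to do with treatment duration, and an inclusion value would remove some of it.

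Three things are at stake: change scores on these scales, the ability to see whether the arms happened to differ on them at entry, and some width of the confidence interval. Section 10.4 lets the analysis plan change until database lock. A measurement that was never taken cannot be added at that stage.

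**Working it through.** **No figure to reproduce.** The plan states no precision, power or SD for PHQ-15 or SF-36. The SD of 2.6 in section 10.1 belongs to the composite score. Everything below is therefore in units of the SD of the six-month score.

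**Inputs.**
- 60 patients per arm (section 4.2), 1:1 allocation (section 10.2.1).
- Significance level 0.05 (section 10.5). Sidedness is not stated; two-sided is assumed.
- Correlation r between the inclusion and six-month scores: not in the documents. I use 0.3 and 0.5. It may lie at the low end, because inclusion falls in acute illness.

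**Formulas (normal approximation).**
- Standard error without an inclusion value: √(2/n)
- Standard error with the inclusion value as covariate: √(1 − r²) × √(2/n)
- 95% half-width: 1.96 × standard error
- Difference detectable with 80% power: (1.96 + 0.842) × standard error
- Number of unadjusted patients giving the same precision: 120/(1 − r²)

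**Half-widths.**
- No inclusion value: √(2/60) = 0.1826; 1.96 × 0.1826 = 0.358 SD.
- r = 0.3: √0.91 × 0.1826 = 0.1742; 1.96 × 0.1742 = 0.341 SD, about 5% narrower.
- r = 0.5: √0.75 × 0.1826 = 0.1581; 1.96 × 0.1581 = 0.310 SD, about 13% narrower.

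| | No inclusion value | r = 0.3 | r = 0.5 |
|---|---|---|---|
| 95% half-width (SD) | 0.358 | 0.341 | 0.310 |
| Detectable difference, 80% power (SD) | 0.511 | 0.488 | 0.443 |
| Power for a 0.5 SD difference | 78.2% | 81.9% | 88.5% |
| Equivalent unadjusted total | 120 | 132 | 160 |

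**With missing data.** If 20% lacked a six-month score (an assumption, leaving 48 per arm), the half-widths would be 0.400, 0.382 and 0.346 SD. The relative gain is the same.

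**Chance imbalance at entry.** With 60 per arm, the difference in inclusion means falls within ±1.96 × √(2/60) = ±0.358 SD (in inclusion-score SDs) in 95% of randomisations. At that limit it would carry r × 0.358 into the six-month difference: 0.107 SD at r = 0.3 and 0.179 SD at r = 0.5. The unadjusted interval already allows for this in the long run, so it is not an additional error. What is lost is the chance to see it and correct for it in this trial.

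**Upper bound on the gain.** These figures compare adjustment for the scale's own inclusion value with no baseline adjustment at all. If baseline FSS or the composite score were already in the model, the remaining gain would depend on the partial correlation of the scale with its own inclusion value given those covariates. In practice it would be expected to be smaller.

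**The case against.** The strongest reply is that an inclusion score would measure the wrong thing. PHQ-15 asks about "different subjective somatic symptoms the last 4 weeks", and patients enter with active neurological symptoms; section 5.6 even allows inclusion after doxycycline has been started. The score would mix acute illness with earlier burden. This stands: an inclusion value reflects pre-illness burden only in part, and the same fact argues for a low r. It does not remove the use of the score as a covariate, provided it is completed before allocation. The protocol already accepts a self-report scale, FSS, at that visit.

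Second, much of the ground is covered elsewhere. The composite score, taken at inclusion and at each later assessment, has ten subjective items restricted to complaints related to the current illness. FSS, comorbidity, medication and symptom duration are also recorded at entry, and section 2.2 cites Norwegian normative data for SF-36. A reader might infer that the trial cannot separate earlier somatic burden from complaints after Lyme neuroborreliosis. The documents do not support that. The gap is limited to these two scales.

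Third, a reader might infer that the synopsis objective "To provide a better understanding of the pathogenesis and long-term complaints, and to search for new biomarkers in LNB" fails for want of these values. Table 1 points elsewhere. It places somatic symptoms and quality of life under the primary objective, and assigns the objective on long-term complaints to antibody, inflammatory and genomic profiles, MRI and neuropsychology. The details are in an appendix that is not part of the documents available here.

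Fourth, collecting the values would change nothing under section 10.5 as written, which names only unadjusted tests for these endpoints and specifies no baseline adjustment even for FSS. This is correct, and the remedy must therefore include the analysis.

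**Conclusion.** The gap is real and consistent across the flow chart and the visit lists: two secondary efficacy endpoints have no inclusion value, while FSS and the composite score do. The consequences are modest. The arm comparison is unbiased and the primary endpoint is not affected. What is lost is any change score on PHQ-15 and SF-36, sight of a chance imbalance on them, and roughly 5% (r = 0.3) to 13% (r = 0.5) in interval width. These percentages rest on an assumed correlation, complete data and no other baseline covariate.

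It would be tempting to conclude that PHQ-15 and SF-36 can neither support nor challenge the primary result. An interval of ±0.358 SD instead of ±0.341 or ±0.310 SD does not show that, and the plan states no margin on either scale against which to judge it. The absence of SF-36 at 12 months is likewise not a fault: six months is the primary time point, and no 12-month SF-36 endpoint is promised.

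This is an optional improvement, worth making because it is cheap and cannot be made afterwards.

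**What to change.** 1. Add PHQ-15 and SF-36 to the inclusion visit in section 6.2.1 and Table 5, next to FSS, to be completed before allocation.
2. In section 10.5, pre-specify that six-month PHQ-15, SF-36 and FSS are each compared between arms by a linear model with the inclusion value of the same scale as covariate, in place of unadjusted tests. For FSS this needs no new data.
3. In section 2.2, state the time points of both scales. It now names only six months for PHQ-15, although Table 5 and section 6.2.6 also give it at 12 months, and it names none for SF-36.
4. Report inclusion scores as a description of patients during acute illness, not as pre-illness values. A short question on whether symptoms began before the current illness would help interpretation but is not essential. SF-36 at 12 months is optional.

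**Cost.** A minor amendment with no new visit or procedure, and roughly 10 to 15 minutes of patient time at inclusion (assumed), at a point when patients are unwell. Patients enrolled before the change will lack the value, so section 10.5 should say how a missing inclusion value is handled.
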